#### Software(s)

All analyses will be performed using Statistical Analysis System (SAS)® Software version 9.4 or higher.

## **10** Study Patients

The subsections in this section include specifications for reporting patient disposition and study dose/study discontinuations. Additionally, procedures for reporting protocol deviations are provided.

## **10.1** Disposition of Patients and Discontinuations

This section describes how patient disposition, study and study dose discontinuations will be summarized. The following disposition categories will be considered.

- Total number of screened patients
- Number of enrolled patients (i.e., those who gave informed consent and met all entry criteria). The corresponding percentage will be calculated using the number of screened Patients as a denominator

For the following categories, the corresponding percentage will be calculated with respect to the number of enrolled patients

- Number of patients who received at least one dose of study treatment
- Number of patients who completed the 24-month study
- Number of patients who discontinued the study treatment, grouped by main reason (reason from last study dose stopped). The percentages for the reasons will be calculated using the number of patients who discontinued the study treatment as denominator
- Number of patients who discontinued the 24-month study, grouped by main reason. The percentages for the reasons will be calculated using the number of patients who discontinued the study as denominator

## **10.2 Protocol Deviations**

The analysis of the protocol deviations will be performed on the FAS, unless otherwise stated. Protocol deviations will be collected in a deviation log.

## **10.2.1** Important Protocol Deviations

The following summary table of important protocol deviations will be provided:

• Frequency table per reason of important protocol deviations

## 10.2.2 Reasons Leading to the Exclusion from an Analysis Population

For Patients excluded from the PP, the reasons for exclusion will be summarized and listed;

- Frequency table per reason of exclusion from the PP population
- Listing of reasons of exclusion from the PP population (The listing will include patient ID and the Reason for exclusion from PP Analysis Set)

## **11** Demographics and Other Baseline Characteristics

If not stated otherwise, summaries will be presented on the FAS and PP populations. Missing values for the Baseline characteristics will be treated as described in section 9, unless otherwise stated.

## **11.1 Demographics**

Demographic characteristics will be summarized using the following information from the Demographics eCRF pages.

- Demographic characteristics
  - Gender: male, female
  - Race: white, black or African American, Asian, Native Hawaiian or other Pacific Islander, American Indian or Alaska Native, other
  - Ethnicity: Hispanic or Latino, Not Hispanic or Latino, Not reported, Unknown
  - Age (years)
  - Age categories:
    - <65 years,
    - $\geq 65$  years:
      - 65-74, 75-84, ≥85
  - Weight.

Specifications for computation:

- Age [years]
  - (date of informed consent date of birth + 1) / 365.25

## 11.2 Medical History

The medical history will be summarized from the "Medical History" eCRF page, using Medical Dictionary for Regulatory Activities (MedDRA), current version, preferred term (PT) as event category and system organ class (SOC) body term as Body System category.

Medical history will be displayed in terms of frequency tables: ordered by primary SOC and PT in alphabetical order.

It is recommended to use the most current MedDRA version at the time of data cutoff.

## **11.3 Other Baseline Characteristics**

Summary statistics will be presented for:

• Elapsed time since diagnosis of MS (years)

- Proportion of patients with MS diagnosis <24 months ( $\ge 24$  months) before study
- Elapsed time since first symptoms of MS (years)
- Baseline PRO data
- Baseline laboratory data
- Baseline data on previous MS DMD use
- Relapses during the previous 2 years (1 year, if MS diagnosis is <24 months)
- ARR (retrospective data)
- Baseline MRI data
- MRI data in the 2 years prior to study enrolment or since MS diagnosis, if diagnosis <24 months
- Past treatment adherence (collected via ePRO: MS-TAQ modified Self-Injectables Version to assess adherence during last previous injectable DMD treatment)
- Pregnancy and comorbid conditions (Human Immunodeficiency Virus [HIV], hepatitis B, hepatitis C, tuberculosis and JCV status).

#### Elapsed time since diagnosis of MS

The elapsed time since diagnosis of MS will be calculated as:

elapsed time since diagnosis of MS (days) = Informed consent date - Initial MS diagnosis date

elapsed time since diagnosis of MS (months) = (Informed consent date - Initial MS diagnosis date)/ 30.4375

elapsed time since diagnosis of MS (years) = (Informed consent date - Initial MS diagnosis date)/ 365.25

It will be summarized descriptively as a continuous variable.

#### Elapsed time since first symptoms of MS

The elapsed time since first symptoms of MS will be calculated as:

elapsed time since first symptoms of MS (days) = Informed consent date - First attack date

elapsed time since first symptoms of MS (months) = (Informed consent date - First attack date)/30.4375

elapsed time since first symptoms of MS (years) = (Informed consent date - First attack date)/365.25

It will be summarized descriptively as a continuous variable.

#### **Relapses during the previous 2 years**

The number of relapses during the previous 2 years (or since MS diagnosis if <2 years) and the duration of these relapses will be summarized descriptively as continuous variables.

#### ARR (retrospective data)

The ARR based on the last 24 months prior to the start of treatment with cladribine tablets will be assessed. The retrospective 24 months ARR for a patient is calculated as

(No. of relapses within 24 months prior to written informed consent for that patient / (30.4375\*24)) \* 365.25

For patients who were diagnosed with MS at least 12 months but less than 24 months prior to written informed consent, the number of relapses since MS diagnosis will be used and the ARR calculation will be:

(No. of relapses since MS diagnosis and prior to written informed consent for that patient / (Informed consent date - Initial MS diagnosis date)) \* 365.25

Such a variable will be summarized descriptively.

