8.2 Secondary Objectives

- To assess PROs, treatment adherence and treatment satisfaction during treatment with cladribine tablets
- To assess treatment patterns (MS treatment prior to transition to cladribine tablets, since MS diagnosis, concomitant treatment for MS during the last 2 years prior to initiation of cladribine tablets (or since MS diagnosis, if diagnosis <24 months), follow-up treatment in case of discontinuation of cladribine tablets)
- To estimate the ARR over the 24-month period prior to initiation of cladribine tablets (or since MS diagnosis, if diagnosis <24 months)

• To collect all serious adverse events (SAEs), adverse drug reactions (ADRs), adverse events of special interest (AESIs) and special situations during treatment with cladribine tablets over a 24-month period

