- Treatment adherence questions, based on modified versions of the Multiple Sclerosis Treatment Adherence Questionnaire (MS-TAQ); data to be collected via ePRO at baseline (modified for self-injectables to assess adherence during last previous injectable DMD treatment) and at the end of Months 1, 2, 13, and 14 (modified for cladribine tablets); a Spanish translation is available to patients.
- Proportion of patients experiencing a relapse. For this study, a relapse will be defined as determined and recorded by the investigator and information on the definition used by the investigator will be collected (see Section 9.1.2.1 for a guide on definition).
- Proportion of patients with relapse associated with hospitalization (relapse as primary diagnosis or reason for hospitalization). For this study, a relapse will be defined as determined by the investigator (see Section 9.1.2.1 for a guide on definition).
- Proportion of patients with relapse associated with glucocorticoid use. For this study, a relapse will be defined as determined by the investigator (see Section 9.1.2.1 for a guide on definition).
- Assessment of previous treatment for MS:
 - Previous DMD(s) received for MS prior to study enrollment, since MS diagnosis
 - Reasons for discontinuation of previous DMD(s)
- Proportion of patients who discontinue cladribine tablets
 - Reason for discontinuation of cladribine tablets
 - Elapsed time to discontinuation after first dose
 - Number of doses and % of planned doses (as per USPI) received
 - Subsequent treatment chosen following discontinuation of cladribine tablets
- Assessment of concomitant MS medications used during study period
- The ARR based on the last 24 months (or since MS diagnosis, if diagnosis <24 months) prior to the start of treatment with cladribine tablets (retrospective data). For this study, a relapse will be defined as determined by the investigator (see Section 9.1.2.1 for a guide on definition).

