9.2.4 Frequency of Assessments

Table 1 lists the Schedule of Assessments. Patients are considered enrolled once the informed consent form (ICF) has been signed prior to any data collection for this study. The Baseline Visit is the visit immediately prior to the patient initiating treatment with cladribine tablets. If the sites anticipate a delay between the decision to start cladribine tablets (i.e. prescription) and patient access to cladribine tablets (i.e. due to delays in cladribine tablets availability or access), the site can perform a Screening Visit first to determine eligibility of the patient and a subsequent Baseline Visit closer to the time the patient starts taking cladribine tablets. Data entered during the Baseline Visit are considered baseline data for the purposes of analysis.

Sites are asked to enter patient follow-up data for up to 24 months after a patient received initial dose if Year 2 treatment course is not delayed and up to 30 months after initial dose if Year-2 treatment course is delayed up to 6 months. Visits will be conducted within the context of routine clinical care; thus, the timing of study visits is approximate and not mandated by the study protocol.

It is anticipated that patients enrolled in the study may not immediately start cladribine tablets after the decision to initiate cladribine tablets is made, owing to the need to first discontinue their current injectable DMD (for a time period determined by the investigator) and to potential delays in obtaining cladribine tablets in the clinical setting. The initial PRO only collection (Month 1) is intended to be obtained after the patient has started treatment with cladribine tablets. The timing of Visit 1 (Month 2) and the subsequent visits may need to be adjusted based upon the actual start date of cladribine tablets, which will be recorded by the investigator.

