Treatment patterns: Prior treatment patterns will be described at baseline (previous DMD treatment(s) and baseline characteristics of patients initiating cladribine tablets). Treatment discontinuation of cladribine tablets and the reasons for discontinuation will be described, as will be the follow-up treatments.

Annualized Relapse Rate (retrospective assessment): The ARR during the last 24 months before starting cladribine tablets (or since MS diagnosis, if diagnosis <24 months) will be presented. accompanied by the respective 95% CIs.

Safety: All safety data (AEs and hematology data, including lymphocyte subtype data, as available) will be evaluated descriptively.

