Other relapse analyses	Proportion of patients experiencing a relapse (24-month and 12-month periods) and ARR over the 12-month period	24-month treatment period (or 30 months if Year 2 treatment is delayed) and 12-month	Section 14.2
	Proportion of patients with relapse associated with hospitalization and ARR associated with hospitalization		
	Proportion of patients with relapse associated with glucocorticoid use and ARR associated with glucocorticoid use	from first dose of cladribine tablets	
To assess treatment patterns (Multiple Sclerosis [MS] treatment prior to transition to cladribine tablets, since MS diagnosis, concomitant treatment for MS during the last 2 years prior to initiation of cladribine tablets (or since MS diagnosis if diagnosis <24 months), follow-up treatment in case of discontinuation of cladribine tablets)	
 
Assessment of previous treatment for MS:         
 
Previous DMD received for MS during the last 2 years
 
Number of previous DMD received for MS (a) during the last 2 years and (b) in total
 
Reasons for discontinuation of last previous DMD
 
 
 
Assessment of concomitant MS medications used during the study period
 
Proportion of patients who discontinue cladribine tablets         
 
Reason for discontinuation of cladribine tablets
 
Elapsed time to discontinuation after the first dose of cladribine tablets
 
Number of doses and % of planned doses of cladribine tablets aproduct Information [USPI]) received
 
 
 
Subsequent treatment chosen following discontinuation of cladribine tablets
 
	For previous treatment: 24- month period prior to initiation of cladribine tablets For concomitant medication, cladribine tablets discontinuation and subsequent treatment: 24- month period from first dose of cladribine tablets (or 30 months if Year 2 treatment is delayed)	Section 11.3 and section 12
To estimate the ARR over the 24-month period prior to initiation of cladribine tablets (or since MS diagnosis if diagnosis <24 months)	The ARR based on the last 24 months prior to the start of treatment with cladribine tablets (or since MS diagnosis if diagnosis <24 months) (retrospective data)	24-month period prior to initiation of cladribine tablets (or since MS diagnosis if diagnosis <24 months)	Section 11.3

Objectives	Endpoints (Outcome Measures)	Endpoints (Outcome Measures) Timeframe	IAP section

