## 7 Changes to the Planned Analyses in the Clinical Study Protocol

There are no changes to the planned analyses.

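### The retrospective ARR is defined over the 24 months before cladribine starts, but both SAP 11.3 formulae end the window at written informed consent

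*SAP*

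**What the plan says.** Every definition of the endpoint ends the window at the start of cladribine:

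- Protocol 8.2 sets the objective: "To estimate the ARR over the 24-month period prior to initiation of cladribine tablets". Protocol 9.1.2.2 gives the outcome the same end point.
- Protocol 9.7.3 describes the analysis as "The ARR during the last 24 months before starting cladribine tablets".
- SAP section 5 lists the endpoint as "The ARR based on the last 24 months prior to the start of treatment with cladribine tablets".
- SAP 11.3, under ARR (retrospective data), opens: "The ARR based on the last 24 months prior to the start of treatment with cladribine tablets will be assessed".

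The two formulae that follow in SAP 11.3 end elsewhere. For patients diagnosed at least 24 months earlier, the numerator is "No. of relapses within 24 months prior to written informed consent for that patient", divided by 30.4375 × 24 days and multiplied by 365.25. For patients diagnosed at least 12 but less than 24 months before consent, relapses are counted from diagnosis to consent and divided by the days from diagnosis to consent. The choice of formula also depends on time from diagnosis to consent.

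SAP section 7 states: "There are no changes to the planned analyses".

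**The concern.** SAP 11.3 states one endpoint and computes another, and nothing in the SAP records consent as a deliberate choice. The difference matters only if consent and first dose fall on different dates, and the plan provides for that. Under protocol 9.2.4 a patient is enrolled on signing the consent form. Sites that expect a delay in access may hold a Screening Visit first and a Baseline Visit closer to treatment. Table 1 places consent in the screening column and the collection of previous relapses at the Baseline Visit, immediately before treatment. Sites can therefore record relapses up to about the first dose, and the formula would then discard the most recent ones.

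The follow-up clock in SAP 14.1.1 starts at first dose. The interval from consent to first dose is thus covered neither by the retrospective formulae nor by time on study, although the stated retrospective endpoint includes it.

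A related count has no anchor at all. The number of relapses in the previous 2 years is summarized in SAP 11.3, is a covariate in the negative binomial and zero-inflated models (SAP 14.1.1 and 14.1.2) and is an imputation variable (SAP 14.1.4). None of these places names the date at which the 2 years end. For patients diagnosed less than 24 months ago, the list at the head of SAP 11.3 uses 1 year, while the paragraph on previous relapses uses the time since diagnosis.

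**Working it through.** The documents give no expected value for the retrospective ARR, so there is no planned figure to reproduce. The check is of window arithmetic.

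**Inputs**

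- SAP section 9: 1 month = 30.4375 days, 1 year = 365.25 days.
- Protocol Table 1: screening, including consent, at Days -45 to 0.
- Gap from consent to first dose: g days. On the schedule g runs from 0 to 45 if first dose falls on the day of the Baseline Visit. Visit timing is not mandated, so 45 is not an enforced maximum.

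**24-month formula**

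- Window: 30.4375 × 24 = 730.5 days. Each relapse adds 365.25 / 730.5 = 0.5 per year, so the constant is internally consistent.
- The window is displaced, not shortened: it reaches back g days too far and stops g days too early.
- Share of the stated window left out: g / 730.5. At g = 15, 30 and 45 this is 2.1%, 4.1% and 6.2%.
- Illustrative patient: one relapse 10 months before consent, one 20 days after consent, first dose 45 days after consent. The formula gives 1 × 0.5 = 0.5 per year; the stated endpoint gives 2 × 0.5 = 1.0 per year.

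**Since-diagnosis formula**

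- Share left out: g / (days from diagnosis to consent + g). For a patient diagnosed 365.25 days before consent and g = 45: 45 / 410.25 = 11.0%.
- Here the rate changes even without a relapse in the gap. Take a diagnosis 400 days before consent, one relapse before consent, g = 45:
  - SAP formula: 365.25 / 400 = 0.913.
  - Ending at first dose, no relapse in the gap: 365.25 / 445 = 0.821.
  - Ending at first dose, one relapse in the gap: 2 × 365.25 / 445 = 1.642.

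**Cohort mean**

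For the 24-month formula, moving the end point to first dose changes the expected mean by (g / 730.5) × (rate in the gap − rate in the early days dropped). The documents give neither rate. The table assumes g = 45 for every patient and a rate of 0.6 per year outside the gap.

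| Rate in the gap, relative to 0.6 | Mean ending at consent | Mean ending at first dose | Change |
|---|---|---|---|
| half | 0.600 | 0.582 | −3.1% |
| equal | 0.600 | 0.600 | 0 |
| double | 0.600 | 0.637 | +6.2% |
| four times | 0.600 | 0.711 | +18.5% |

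With shorter gaps these changes shrink in proportion, and at g = 0 they vanish.

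**The case against.** The strongest reply is that little depends on this. The retrospective ARR is summarized descriptively, no before/after test is planned, the Screening Visit is optional, and with no gap or equal rates the expected mean does not move. All of that stands, and it limits the weight of the point.

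A second reply concerns the evidence for a gap. Protocol 9.2.4 says "It is anticipated that patients enrolled in the study may not immediately start cladribine tablets", but the sentence goes on to measure the delay from the decision to treat. Under inclusion criterion 7 that decision comes before enrolment, so part of the delay may precede consent. This also stands: the sentence shows that delay is expected, not how much of it follows consent. The optional Screening Visit and the Days -45 to 0 column still allow a gap after consent.

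A third reply is that consent is used consistently in SAP 11.3 for time since diagnosis, time since first symptoms and the <24-month rule for MRI and prior treatment. That is a reason to weigh the two anchors. It does not reconcile the formulae with the endpoint as defined.

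Two stronger readings are tempting. A reader might infer that the consent-based formula also sets the prior-relapse class (≤1 or >1) in the sensitivity models. It does not: the formula defines a rate, and SAP 14.1.1 and 14.1.2 do not refer to it. Those sections only leave the end date open. A reader might also infer that the primary ARR is wrong and needs a new cut by onset date. SAP section 5 and the time-on-study definition in 14.1.1 already start it at first dose. Such a cut could do harm if it used the partial-date rule in SAP section 9, which sets a missing month as well as a missing day to 1. An on-study relapse could then be dated before first dose and lost.

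**Conclusion.** The mismatch is real and should be corrected. Both formulae and the rule choosing between them end at consent, while the protocol, SAP section 5 and SAP 11.3's own lead sentence end at the start of cladribine, with no change declared. The displacement ranges from 0 to 45 days on the schedule: at most 6.2% of the 24-month window, or 11.0% for a patient diagnosed 12 months before consent. Because timing is not mandated, actual gaps could be longer. A single patient's rate can differ by 0.5 per year or more. The effect on the cohort mean cannot be determined from the documents and may be zero; the percentages above rest on assumed rates and a 45-day gap for everyone. The effect is confined to a secondary, descriptive endpoint, with a separate ambiguity in the prior-relapse count. The primary ARR estimate is not affected.

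**What to change.** In both SAP 11.3 formulae, and in the <24-month rule that chooses between them, replace written informed consent with the date of first dose of cladribine tablets. The 24-month formula keeps its 730.5-day denominator; the since-diagnosis denominator becomes first-dose date minus diagnosis date. Count relapses by onset date before first dose, from the relapse data already collected, and state that each relapse is counted in only one of the two ARR windows.

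Use the same first-dose anchor for the prior-relapse count in SAP 11.3, 14.1.1, 14.1.2 and 14.1.4. In SAP 11.3, bring the 1-year wording for recently diagnosed patients into line with the since-diagnosis wording.

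If the sponsor prefers consent as the anchor, the fallback is to restate the endpoint as the period before informed consent and list the change in SAP section 7.

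The cost is a handful of text edits and no new data, since protocol 9.3 already collects cladribine start dates and relapse onset dates. The drawback is mixed anchors: time since diagnosis, time since first symptoms, and the MRI and prior-treatment summaries would stay on consent or enrolment. With a 45-day gap (45 / 30.4375 = 1.5 months), a patient diagnosed between 22.5 and 24 months before consent would be under 24 months in the MRI and prior-treatment tables but at or above 24 months in the ARR table. A table footnote should say so.

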#### Baseline PROs, laboratory and MRI data.

Baseline PROs, laboratory, and MRI data is anticipated to be collected before the first dose of cladribine tablets is taken.

Baseline PROs and laboratory data will be summarized descriptively as continuous variables.

Most recent MRI prior to starting cladribine tablets (baseline MRI), which is expected to have been taken within the prior 90 days, will be summarized descriptively considering the following continuous variables:

- number of T1 Gd+ lesions;
- number of new T2 lesions compared to most recent prior MRI;
- number of newly enlarging T2 lesions compared to most recent prior MRI;
- number of Combined Unique (CU) lesions;

and the following qualitative variables:

- presence of brain atrophy;
- presence of segmental atrophy.

Results of MRI in the 2 years prior to study enrolment will be summarized descriptively with respect to the above continuous variables for the lesions. The number and percentage of patients with brain atrophy or segmental atrophy in the previous 2 years will be reported. For patients who

were diagnosed with MS less than 24 months prior to written informed consent, MRI results since diagnosis will be summarized.

